**Table 6: Derivation rules for failure rate at 6 months in patients with stage 2 HAT**

|   |  |
|---|--|
| Outcome at M6
for the 3 rd futility
analysis | Patient is dead (any reason) before M6 $\Rightarrow$ Failure (stop)   |
|   | $\Downarrow$   |
|   | Alive  |
|   | $\Downarrow$   |
|   | Patient requires rescue medication for HAT $\Rightarrow$ YES $\Rightarrow$ Failure (stop)   |
|   | $\Downarrow$   |
|   | NO rescue medication up-to M6  |
|   | $\Downarrow$   |
|   | Evidence of trypanosomes in any body fluid at M6 or between drug intake and M6 visit $\Rightarrow$ YES $\Rightarrow$ Failure (stop)   |
|   | $\Downarrow$   |
| Outcome at M6
for the 3 rd futility
analysis | NO   |
|   | $\Downarrow$   |
|   | Patient Lost to follow-up before M6 $\Rightarrow$ YES $\Rightarrow$ Failure (stop)  |
|   | $\Downarrow$   |
|   | NO   |
|   | $\Downarrow$   |
|   | WBC in CSF at M6 $\leq$ 20 cells and no signs and symptoms related to HAT at M6
$\Rightarrow$ YES $\Rightarrow$ Success (stop)   |
|   | $\Downarrow$   |
|   | NO   |
|   | $\Downarrow$   |
| Outcome at M6
for the 3 rd futility
analysis | WBC in CSF at M6 $>$ 50 cells $\Rightarrow$ YES $\Rightarrow$ Failure (stop)  |
|   | $\Downarrow$   |
|   | NO   |
|   | $\Downarrow$   |
|   | Evidence of trypanosomes at M12 $\Rightarrow$ YES $\Rightarrow$ Failure (stop)  |
|   | $\Downarrow$   |
|   | NO   |
|   | $\Downarrow$   |
|   | WBC in CSF at M12 $\leq$ 20 and no signs and symptoms related to HAT at M12:
$\Rightarrow$ Success (stop)  |
|   | $\Downarrow$   |
| Outcome at M6
for the 3 rd futility
analysis | WBC in CSF at M12 $>$ 50 $\Rightarrow$ Failure (stop)   |
|   | $\Downarrow$   |
|   | WBC in CSF at M12 between 20 and 50:

$\Rightarrow$ WBC in CSF at M12 $\geq$ M6 (i.e. increase) $\Rightarrow$ YES $\Rightarrow$ Failure (stop)
$\Rightarrow$ WBC in CSF at M12 $<$ M6 (i.e. decrease):

$\Rightarrow$ WBC in CSF at M18 $\leq$ 20 and no trypanosomes at M18 and no signs/symptoms at M18 $\Rightarrow$ Success (stop)
$\Rightarrow$ WBC in CSF at M18 $>$ 20 or trypanosomes at M18 $\Rightarrow$ Failure (stop) |
|   | $\Downarrow$   |
|   | Otherwise: Not evaluable  |
|   |  |
|   |  |
|   |  |
|   |  |
|   |  |

**Additional futility analyses:**

Additional futility analyses may be performed if deemed necessary during the course of the study.

**Rules for Success of the Study:**

There are no objective rules for the success of the study. As recommended by the EMA Scientific Advice Working Party, the observed success rate and lower bound of the 95% CI will be interpreted in light of those obtained in the literature and historical data, taking into account the obvious advantage of having a single oral dose for patients living in remote areas.

**8.8. Safety analysis**

All safety analyses will be performed on the Treated set.

**8.8.1. Adverse events**

Analysis of adverse events will be based on the concept of treatment-emergent adverse events (TEAE) (cf. definition in [Section 6.3.1](#)).

An overall summary of TEAEs occurring during the 18 months follow-up period (i.e. from first drug intake up-to end of follow-up) will be presented by cohort, by stage of disease and overall. The following information will be tabulated (the number, percentage of patient and 95% CI):

- At least one AE
- At least one TEAE
- At least one mild/moderate TEAE (grade 1, grade 2, mild or moderate)
- At least one severe TEAE (grade 3, grade 4, grade 5 or severe)
- At least one drug-related TEAE
- At least one serious TEAE
- At least one serious drug-related TEAE

For the following descriptions the number and percentage of patients and the number of occurrences of TEAE will be presented by cohort, by period of occurrence, by stage of disease and overall, and by MedDRA SOC and PT (descending order of SOC and PT):

- TEAE
- Drug-related TEAE
- Serious TEAE
- Serious drug-related TEAE
- TEAE of interest

All AEs and SAEs will be listed.

**8.8.2. Laboratory examination****Descriptive analysis at baseline, at each time points and changes from baseline:**

For continuous data, a descriptive analysis will be provided for baseline, at each time point and for the changes from baseline at each time point by cohort, by stage of disease and overall.

**Shift tables according to lower and upper limits of normal range:**

For all laboratory parameters (except ASAT, ALAT and TSH), shift tables according to lower and upper limits of normal range (<LLN, Normal, >ULN) between baseline and each time point (i.e. D5, D11, M3, M6, M12, M18) for each laboratory parameters will be provided by cohort, by stage of disease and overall. On exploratory purpose, Bowker's symmetry test will be performed.

The same analysis will be provided for ASAT and ALAT using the following classes: <0.5\*LLN, [0.5\*LLN to <LLN, Normal, >ULN to 2\*ULN], >2\*ULN to 3\*ULN], >3\*ULN).

The same analysis will be provided for TSH using the following classes: <0.5\*LLN, [0.5\*LLN to <LLN, Normal, >ULN to 2\*ULN], >2\*ULN).

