--	--

	
(dependent variable) and two covariables (explanatory variables): blood and CSF concentrations.
 
 
▪ Changes in the rate of favourable outcomes over time for late-stage patients on the one hand, and for early- and intermediate-stage patients on the other hand, will be studied using the mixed model for repeated measures (Glimmix).
 
▪ Time to proven relapse will be analysed in each cohort using the Kaplan-Meier approach in order to estimate, at each follow-up visit, the cumulative rate of proven failures. Patients lost to follow-up will be censored at the last available visit, unless the outcome at that visit was failure.
 
 
Safety Analyses
 
All patients who received acoziborole will be included in the safety analyses.
 
The percentage of patients who experienced a serious adverse event (SAE) will be described by system-organ class.
 
The percentage of patients who experienced at least one adverse event will (AE) be described. Each SAE will be described in a narrative presenting all aspects of the medical event and the causality assessment.
 
The incidence of AEs and of SAEs and their respective 95% confidence intervals will be presented by category and by frequency. In other cases, only descriptive statistics will be presented.
 
Laboratory safety parameters, i.e. haematology and biochemistry, will be described individually, indicating the percentages of patients by the size of the increase in relation to the ULN and to baseline values, as well as changes in blood levels over time. Shift tables will be provided. A listing of patients with increases in laboratory parameters will be provided.
 
Abnormalities on electrocardiogram (ECG) tracings will be described for each timepoint.
 
Futility Analyses
 
An independent Data and Safety Monitoring Board (DSMB) will be appointed, among other things, to supervise and review the futility and PK analyses, as well as the safety data. The DSMB will make recommendations on study continuation based on all available information.
 
The first futility analysis will be performed once the first 20 late-stage patients reach the 3-month visit. If the failure rate at Day 11 is significantly higher than the failure rate for melarsoprol (19), the study should be stopped for futility and for ethical reasons. The failure rate for melarsoprol at the end of treatment was 5% (4.8% for N = 6840). If 4 patients out of 20 are failures at Day 11 (<math>p = 0.0159</math>), then the DSMB should recommend stopping the study, unless the rate can be explained by exceptional circumstances.
 
The second futility analysis will be performed once 70 late-stage patients reach the 3-month visit. The recommendation to

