### **6.5.2. Definition of Serious Adverse Event**

An SAE is any event that:

- results in death;
- is life-threatening;
- requires hospitalisation or prolongation of existing hospitalisation:
  - i.e. the AE requires admission for at least 24 hours or prolongs hospitalisation beyond the expected length of stay. Hospital admissions for surgery planned before study entry, for social reasons, for any elective surgery (e.g. plastic surgery) or for normal disease management (including treatment adjustment) will not be considered as SAEs;
- results in persistent or significant disability or incapacity;
- is a congenital anomaly or birth defect;
- is an important medical event in which the patient is not at risk of death or which does not directly result in death or hospitalisation, but which may jeopardise patient safety or may require an intervention to prevent one of the above-mentioned outcomes;
- In this study, ALT or AST above 3 ULN accompanied by total bilirubin above 2 ULN will be considered as an SAE;
- Any suspected transmission of an infectious agent via a medicinal product will also be considered as an SAE.

Any other event defined as serious in this protocol or by the Regulatory Authorities in the countries where the study is being conducted will also be considered as an SAE.

For the purposes of this study, hospitalisation for uncomplicated delivery will not be considered as an SAE.

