## 9.7. Safety Analyses

All patients who received at least one tablet of acoziborole will be included in the safety analyses.

The percentage of patients who experienced an SAE will be described by system-organ class using MedDRA terms and/or according to NCI CTCAE, version 4.03 (16).

The percentage of patients who experienced at least one AE will be described. Events described with the same term and that occur several times in the same patient will be counted only once. If a patient experiences several events described with the same term, the event with the maximal severity will be included in the analysis. In addition, each SAE will be described in a narrative presenting all aspects of the medical event and the causality assessment.

The incidence of AEs and of SAEs and their respective 95% confidence intervals will be presented by category and by frequency. In other cases, only descriptive statistics will be presented.

Laboratory safety parameters, i.e. haematology and biochemistry, will also be described individually, indicating the percentages of patients, the size of the increase in relation to the ULN and to baseline values, as well as changes in blood levels over time. Shift tables will be provided. A listing of patients with increases in laboratory parameters will be provided.

Abnormalities on ECG tracings will be described for each timepoint.

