#### **16.2.9 Individual laboratory measurements**

- Note: listing of individual laboratory measurements (i.e. Haematology, Biochemistry, Thyroid function) will be provided in an excel file.

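### The SAP gives total bilirubin a single class above ULN and derives no count of the combined liver criterion that the protocol defines as an SAE; the departure from Protocol 9.7 is not declared

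*SAP*

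**What the plan says.** Protocol 9.7 asks for haematology and biochemistry to be described individually, "indicating the percentages of patients, the size of the increase in relation to the ULN and to baseline values". The Protocol Summary is more explicit: "indicating the percentages of patients by the size of the increase in relation to the ULN and to baseline values". Protocol 9.7 also promises shift tables and adds "A listing of patients with increases in laboratory parameters will be provided".

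Protocol 6.5.2 sets a laboratory-based seriousness criterion: "In this study, ALT or AST above 3 ULN accompanied by total bilirubin above 2 ULN will be considered as an SAE".

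The SAP handles laboratory data as follows.
- Section 6.5.4 classifies continuous values as below, within or above the reference range, with no multiples of ULN.
- Section 8.8.2 repeats this for the shift tables: "For all laboratory parameters (except ASAT, ALAT and TSH), shift tables according to lower and upper limits of normal range (<LLN, Normal, >ULN". AST and ALT have graded classes up to more than 3 ULN, and TSH up to more than 2 ULN. The output list in 9.1.7 matches.
- Total bilirubin takes the default classes. It also has a descriptive table whose template (9.2.25) shows the maximum at each visit. The output list adds a scatterplot for every biochemistry parameter, although 8.8.2 does not name bilirubin among the parameters to be plotted.
- Under output 16.2.9, individual laboratory measurements "will be provided in an excel file".
- Section 11 declares changes to adverse event counting, stage wording and the NECT yardstick. Laboratory grading is not among them.

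**The concern.** A single class above ULN says that a value rose out of range but not by how much. That falls short of what Protocol 9.7 asks for, and the SAP does not say that it departs.

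The gap matters most for total bilirubin. The protocol makes a specific combination of transaminase and bilirubin elevation an SAE, and both limits are laboratory values that the study collects. One would expect the analysis to derive that criterion from the data. As planned, the transaminase half is tabulated, the bilirubin half is not, and nothing joins the two within a patient. Whether a case is counted then depends on the site having recognised and reported it. The final safety statement could say that no patient met the criterion without anyone having checked the laboratory data for it.

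**Working it through.** The documents give no figure on this point, so the check is a comparison of texts and a count.

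**Parameters graded by multiples of ULN** (listed in SAP 9.1.7, classes from 8.8.2)

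| Group | Listed | Graded |
|---|---|---|
| Haematology | 8 | 0 |
| Biochemistry | 14 | 2 (AST, ALT) |
| Thyroid | 3 | 1 (TSH) |
| All | 8 + 14 + 3 = 25 | 3 |

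The sentence in Protocol 9.7 covers haematology and biochemistry: 8 + 14 = 22 parameters, of which 2 are graded.

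**Bilirubin.** In the shift table, 1.1 ULN and 5 ULN fall in the same cell. The limit of 2 ULN in Protocol 6.5.2 cannot be read from it.

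**The combined criterion, output by output**

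1. *AST and ALT shift tables:* show patients above 3 ULN at each tabulated visit, but not their bilirubin.
2. *Bilirubin descriptive table:* gives a maximum per visit, which would draw attention to an extreme value. It gives no count above 2 ULN and no link to transaminases.
3. *Bilirubin scatterplot (output list only):* shows individual values against baseline, again with no link.
4. *Laboratory listing:* holds all the values needed, but no flag is specified.
5. *SAE listing and serious TEAE tables (SAP 8.8.1):* a reported case appears under its system organ class and preferred term, without being identified as meeting this criterion. An unreported case does not appear.
6. *TEAEs of interest (SAP 6.4.1):* optional, to be defined at the data review meeting, with no liver category named.

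**Can a peak be lost from the tables?** SAP 7.5 applies time-windows to laboratory data and, when two visits fall in one window, uses the latest. It also states that retests are recorded as unscheduled visits. The 3-month window in SAP Table 3 runs from D19 to D136 around a theoretical D91. If a raised value at D91 is retested by D136, the retest replaces it. The peak then drops out of outputs 1 to 3, for AST and ALT as well as bilirubin. It survives only in the listing.

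**The case against.** The strongest defence is that the SAP made a risk-based choice. Protocol 1.7 reports transaminase elevations (with placebo too) and thyroid variations in Phase I, and no abnormality of bilirubin, creatinine or haematology in exposed subjects. Grading AST, ALT and TSH follows that pattern. Moreover, AST or ALT above 3 ULN is a necessary condition for the SAE. If those cells are empty, no case exists; if not, a few patients can be checked in the listing. Protocol 9.7 speaks of size relative to ULN, not of multiples, and change from baseline is tabulated for every parameter. Clinically significant abnormalities above CTCAE grade 1 must be reported as adverse events (Protocol 6.5.1), and centralised monitoring and the DSMB add further checks.

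Much of this stands. Phase I gives no specific reason to expect a bilirubin signal, and a complete Excel listing contains every patient whom the protocol's listing would contain; only the flag is missing.

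Two parts do not stand. A single class above ULN conveys no size, however the phrase in Protocol 9.7 is read. The necessary-condition argument also fails when the latest-in-window rule has removed the transaminase peak. The other safeguards reduce the chance of a missed case, but Protocol 11.3 states that source verification will not be complete, and neither document specifies a reconciliation of laboratory values with SAEs.

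A reader might infer that a marked bilirubin rise would be invisible, or that cases have been missed. The documents support neither: maxima, an output-list scatterplot and raw values are planned, and nothing suggests that a case occurred.

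**Conclusion.** The point holds in a limited form. The SAP grades 2 of the 22 parameters covered by Protocol 9.7 and does not declare this. It gives no count of bilirubin above 2 ULN and no derivation of a protocol-defined SAE from the laboratory data. Site-reported cases would be seen as SAEs; an unreported one would not be counted. This is a gap in safety reporting that should be closed. It does not touch the primary efficacy estimate.

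The conclusion rests on the SAP text and output list as written. The DSMB charter and monitoring plan are not available and might contain a reconciliation step.

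Three stronger readings are not supported.
- The eligibility limit for bilirubin of 1.5 ULN in Protocol 4.3 is not something the post-dose shift tables need to show.
- The protocol sets no numeric limit for alkaline phosphatase or creatinine, so specific grades for them would be a preference.
- A zero-event confidence limit does not measure this gap, because it is the same whichever tables are made. For context only, assuming that all 162 late-stage and about 50 other patients are treated (162 + 50 = 212), no cases would give a two-sided 95% upper limit of 1 − 0.025^(1/162) = 2.3% for late-stage patients and 1 − 0.025^(1/212) = 1.7% overall.

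**What to change.** 1. In SAP 8.8.2 and 9.1.7, add a class above 2 ULN to the total bilirubin shift tables.
2. Add, on the Treated set, a patient-level count and a flagged listing of post-dose ALT or AST above 3 ULN with total bilirubin above 2 ULN. Use all post-dose values, including unscheduled ones, without the latest-in-window rule. Require both limits to be exceeded at the same sampling visit, or within an interval stated in advance. Crossing each patient's maximum transaminase with maximum bilirubin should not serve as the definition, because it can pair values months apart while Protocol 6.5.2 requires one to accompany the other.
3. Reconcile that listing with the SAE database before database lock.
4. For the remaining haematology and biochemistry parameters, either grade increases relative to ULN or declare the departure from Protocol 9.7 in SAP Section 11.

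The thresholds are the protocol's own and the data are already collected. The cost is a few extra outputs, one reconciliation step and, if that route is taken, a short entry in Section 11.

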**Scatterplots:**

Scatterplots between baseline value and value at each of the following time point: D5, D11, M3, M18 for the following laboratory parameters: ASAT, ALAT, Potassium, Bicarbonates, Albumin and TSH will be provided by cohort.

**8.8.3. Pharmacokinetics**

The statistical analysis will be performed by [REDACTED] and will be described in a separate statistical analysis plan.

**8.8.4. Electrocardiogram**

The statistical analysis will be performed by [REDACTED] and will be described in a separate statistical analysis plan.

**8.9. Analysis of other endpoints and variables**

Analyses of other endpoints will be performed on the Treated set. Results will be displayed by cohort, by stage of disease and overall.

**8.9.1. Vital signs**

Descriptive statistics will be provided by visit.

In addition, descriptive statistics of changes in weight (kg) from baseline and relative change from baseline in body weight (%) will be provided by visit.

**8.9.2. Clinical signs and symptoms of HAT**

Descriptive statistics will be provided by visit.

**8.9.3. Physical examination**

Descriptive statistics will be provided by visit.

**8.9.4. Neurological examination**

Descriptive statistics will be provided by visit.

**8.9.5. HAT diagnosis (i.e. examination of blood, lymph and CSF samples)**

Descriptive statistics will be provided by visit.

**8.10. Unscheduled visit**

As described in [Section 7.5](#), data from unscheduled visits will be used in the calculation of time-windows and calculated visits.

Data from unscheduled visits will be tabulated in data listings

## 8.11. Data and Safety Monitoring Board (DSMB)

As per protocol, Section 10: a DSMB, composed of at least 3 members independent of the Investigators and the Sponsor, will be set up prior to the start of the study. The DSMB will monitor the study in order to minimise any risk of harm to the patients included in the study.

At each of its meetings, the DSMB will examine safety data and all information related to SAEs, and will issue recommendations regarding the study if the benefit-to-risk ratio for patients seems to be in jeopardy. The data and the intervals for review will be decided before, or shortly after the start of the study and will be recorded in the DSMB Charter.

The results of the futility analyses will be presented to the DSMB, who will decide whether or not the study can continue and whether the enrolment period should be extended.

The organisation of the DSMB will be described in the DSMB Charter, which will be prepared and approved prior to the first planned futility analysis.

Additional ad hoc members may be invited to join the DSMB if any safety concerns emerge, in order to give additional support to the competencies already present.

## 8.12. Analysis of potential biases

In order to assess a potential selection bias, descriptive statistics will be provided on all patients treated and on all patients NOT treated (but with a confirmation of the presence of trypanosomes in any body fluid) for:

- Demographic data
- Vital signs at baseline
- Clinical signs and symptoms of HAT at baseline
- Physical examination at baseline
- Neurological examination at baseline
- HAT diagnosis (i.e. examination of blood, lymph and CSF samples)

This analysis will be performed if at least 5 % of screened patients are not included in the study.

## 9. DISPLAY PLAN

### 9.1. List of Tables, Figures and Listings

Note: outputs listed below should be numbered as described. Sections 14.1, 14.2 and 14.3 may be provided in separate documents, if required. Sections 16.2.1 to 16.2.10 will be provided in separate documents.

#### 9.1.1. List of outputs for ICH Section 14.1 (Study patients)

##### 14. STATISTICAL ANALYSIS

###### 14.1 Study patients

###### 14.1.1 Disposition of patients

14.1.1.1: Disposition of patients by cohort, stage of disease and overall (all patients)

Cf. section 9.2.1, template 1.

14.1.1.2: Disposition of patients: study key dates and study duration (all patients)

Cf. section 9.2.1, template 2.

###### 14.1.2 Protocol deviations

14.1.2.1: Protocol deviations by cohort, stage of disease and overall (mITT)

###### 14.1.3 Analysis sets and subgroups

14.1.3.1: Analysis sets by cohort, stage of disease and overall (all patients)

14.1.3.2: Analysis subgroups (mITT)

###### 14.1.4 Demographic data and other baseline characteristics

14.1.4.1: Demographic data by cohort, stage of disease and overall (mITT)

14.1.4.2: Vital signs at baseline by cohort, stage of disease and overall (mITT)

14.1.4.3: Clinical signs and symptoms of HAT at baseline by cohort, stage of disease and overall (mITT)

14.1.4.4: Physical examination at baseline

